## **5 SAMPLE SIZE DETERMINATION**

### **5.1 Randomization Schema**

The original study design (before Amendment 08) had 2 arms, with subjects being randomized in a 1:1 ratio to the nivolumab plus ipilimumab or to the oxaliplatin plus fluoropyrimidine arm (XELOX or FOLFOX; arm will be further referred to as chemotherapy arm). Amendment 08 added a new arm: nivolumab in combination with oxaliplatin plus fluoropyrimidine (XELOX or FOLFOX; arm will be further referred to as nivolumab plus chemotherapy arm). The IRT switched to a 1:1:1 randomization at all the participating sites when this third arm was ready to be opened on 27-Mar-2017. Up until that point, there were 83 subjects randomized in the 1:1 randomization to nivolumab plus ipilimumab and chemotherapy arm. In Amendment 08, it was planned to randomize 1266 subjects at 1:1:1 ratio to nivolumab plus ipilimumab, chemotherapy and nivolumab plus chemotherapy arms. The total number of subjects to be randomized was planned to be 1349.

Newly available internal and external data suggested a stronger predictability of PD-L1 CPS than TPS of immunotherapy treatment effects. However, uncertainty still exists of CPS at different cutoffs when extrapolated to first line metastatic setting in GC and GEJ. To ensure sufficient sample size for evaluating the correlation of efficacy and different CPS cutoffs and to keep continuity of enrollment of the study, on 29-May-2018, Amendment 19 was approved to allow additional 300 subjects to be randomized under 1:1:1 ratio for a total sample size of 1566 to the 3 treatment arms.

Per DMC recommendation, randomization to the nivolumab plus ipilimumab arm was stopped on 05-June-2018. The subjects who were already randomized to treatment in this arm prior to or on

05-June-2018 continued to receive study treatment per protocol, and the study data remained blinded for the planned analysis. As such, the 1:1:1 randomization was carried through on 05-Jun-2018. These changes were implemented in Amendment 20. At this point, a total of 1098 subjects were randomized under 1:1:1 ratio. In addition, there were 83 subjects randomized to nivolumab plus ipilimumab and to chemotherapy arms (prior to Amendment 08). Following Amendment 20, subjects were to be randomized in 1:1 ratio to either the nivolumab plus chemotherapy or the chemotherapy arm.

In November 2018, data suggested that the PD-L1 CPS  $\geq 5$  prevalence was  $\sim 27\%$  (unpublished data), which was lower than the original estimate of 35%. Therefore, the enrollment was extended to ensure that the study was appropriately powered for PFS and OS primary endpoints in the CPS  $\geq 5$  population. To allow for this, Amendment 26 increased the total sample size from 1649 to approximately 2005. This resizing of the total population was to ensure that the sample size of the enriched population for the primary analyses (subjects with CPS  $\geq 5$ ) was the same as was specified in Amendment 23 to maintain the same power under the statistical assumptions as stated in Amendment 23.

The accrual was completed in May 2019 and in total 2031 subjects were randomized. It is estimated that 1582 subjects were concurrently randomized to nivolumab plus chemotherapy and to chemotherapy and that 815 subjects were concurrently randomized to nivolumab plus ipilimumab and chemotherapy.

Table 5.1-1 present the randomization schema and sample size.

**Table 5.1-1: Randomization Allocation and Sample Size**

Protocol Periods	Randomization allocation	Number of Randomized Subjects Current / Cumulative
First patient randomized - Amendment 8	1:1 (Nivolumab +Ipilimumab: Chemotherapy)	83/83
Amendment 08 - Amendment 20	1:1:1 (Nivolumab + Ipilimumab: Chemotherapy: Nivolumab + Chemotherapy)	1098/1181
Amendment 20 to amendment 26	1:1 (Chemotherapy: Nivolumab + Chemotherapy)	468/1649
Amendment 26 to the end of enrollment	1:1 (Chemotherapy: Nivolumab + Chemotherapy)	382/2031

### **5.1.1 Changes of Statistical Analyses and Timing of Analyses in Protocol Amendment 29**

Per protocol Amendment 23 (November 2018), the primary population of both primary endpoints PFS and OS was changed to randomized subjects with PD-L1 CPS  $\geq 5$  and the PD-L1 CPS scoring process started for subjects already randomized in the study to date. In March 2019, the need for additional steps for the PD-L1 CPS scoring process was established and consequently the expected

completion date of PD-L1 CPS scoring will be delayed and is now projected to complete approximately 6 months or later after the completion of enrollment.

Recent data in 1L GC Phase 3 study suggested a longer delay of separation of KM curves of immuno-oncology drug plus chemo vs chemo for PFS and OS. These data suggested that a longer follow-up would warrant to fully capture of the treatment effect for the primary endpoints of PFS and OS in the N+CT vs. CT.

Considering the delay of completion of PD-L1 CPS scoring, and the need to have longer minimum follow-up for PFS and OS to ensure data maturity, Amendment 29 documents the changes on the timing of PFS and OS analyses from event driven to time driven. In addition, Amendment 29 specifically, documents the changes of the primary population of PFS.

The primary analysis of PFS in randomized subjects with PD-L1 CPS  $\geq 5$  will be conducted after a 12-month minimum follow-up (from the date last patient was concurrently randomized to N+CT or CT). The primary analysis of OS in randomized subjects with PD-L1 CPS  $\geq 5$  includes one interim and final analysis. The interim analysis will be conducted after 12-month minimum follow-up along with the primary PFS analysis. The final OS analysis will be conducted after a 24-month minimum follow-up, ie, 12 months after the OS interim analyses.

The analysis of OS in N+I vs. CT in randomized subjects with PD-L1 CPS  $\geq 5$  will be conducted at approximately 36-month minimum follow-up (after the last patient was randomized to N+I or CT). This analysis will be at the time of the final analysis of N+CT vs. CT.

The timing of the efficacy analyses is described in [Table 1-1](#).

For the primary analyses of the endpoints stated above, all events observed in the locked database will be used.

As of May 2019, study enrollment has been completed. Therefore in Amendment 29, the total sample size was fixed; however, the sample size for the primary population (subjects with PD-L1 CPS  $\geq 5$ ) remained unknown as CPS scoring was still ongoing. The prevalence was assumed to be 35% consistent with sample size and power calculations in Amendment 23. Sections 8.1.4 and 8.1.5 of the Protocol were updated to reflect design characteristics for time driven analyses and using 35% prevalence for PD-L1 CPS  $\geq 5$ .

## 5.2 General Assumptions of Sample Size Determinations

### **Primary Endpoints Family:**

For the comparison of nivolumab plus chemotherapy vs. chemotherapy both PFS and OS are primary endpoints.

### **Type I Error Splitting for Primary Endpoints Family:**

For sample size calculation purpose, the family-wise error rate of 5% will be split as follows:

- 1) Comparison of PFS between nivolumab plus chemotherapy and chemotherapy in subjects with PD-L1 CPS  $\geq 5$ , with alpha of 2%

- 2) Comparison of OS between nivolumab plus chemotherapy and chemotherapy in subjects with PD-L1 CPS  $\geq 5$ , with alpha of 3%

**Population for Primary Endpoints:**

[figure not shown]
The population for the primary endpoints will be randomized subjects with PD-L1 CPS  $\geq 5$ . For the design purpose, the prevalence was assumed to be 35% of all randomized subjects and is used the power statement in Sections 5.2.1 and 5.2.2

**Concurrently Randomized:**

For the comparison of nivolumab plus chemotherapy and chemotherapy only subjects who were randomized to those 2 arms concurrently will be used. This means subjects randomized to chemotherapy before the nivolumab plus chemotherapy arm was introduced will not be included in the analysis of this comparison.

For the comparison of nivolumab + ipilimumab and chemotherapy only subjects who were randomized to those 2 arms concurrently will be used. This means subjects randomized to chemotherapy after the closure of nivolumab plus ipilimumab randomization will not be included in the analysis of this comparison.

**Figure 5.2-1: Randomization Schema**

[figure not shown]
**Assumptions for Control Arm of Chemotherapy:**

In previous protocol versions (up to amendment 20), PD-L1  $\geq 1\%$  per TPS was assumed as negative prognostic factor (ie, the median OS for chemotherapy was assumed to be smaller for subjects with tumor PD-L1  $\geq 1\%$  per TPS than for all randomized subjects). However, for PD-L1 CPS, recent data does not suggest such a negative prognostic effect for chemotherapy. Therefore, in Amendment 23, the OS and PFS distributions for the chemotherapy arm are assumed to be the same regardless of CPS cutoffs, eg, in PD-L1 CPS  $\geq 5$  and in all randomized subjects.

[figure not shown]

The PFS and OS data from the external data were considered the most relevant to the studied chemotherapy arm (control). Therefore, the chemotherapy arm is assumed to have a 4-piece exponential distribution with a median PFS of 5.5 months (see Figure 5.2-2) and a 4-piece exponential distribution with a median OS of 11.1 months (see Figure 5.2-3).

**Figure 5.2-2: PFS for Chemotherapy from External Data and Assumed Distribution for Chemotherapy**

**Figure 5.2-3: OS for Chemotherapy from External Data and Assumed Distribution for Chemotherapy**

**Statistical Software for Sample Size Calculation**

Sample size calculations of the primary endpoints were based on simulations in EAST 6.4.1. Sections 5.2.1 and 5.2.2 describe the sample size and power as stated in protocol.

**5.2.1 Sample Size: Nivolumab plus Chemotherapy vs. Chemotherapy**

**Progression Free Survival**

Concurrently randomized subjects to nivo+chemo and chemo arms with PD-L1 CPS  $\geq 5$  will be used for the PFS analysis. Given the delayed separation in the PFS distributions between pembrolizumab + chemotherapy and chemotherapy, the PFS analysis will be conducted after a minimum of 12 months follow-up after the last patient is randomized.

As such, the PFS analysis will be conducted after the following criteria are all met:

- CPS scoring by central laboratories is complete
- a minimum follow-up of 12 months

The HR is modelled as a 2-piece hazard ratio with a delayed effect of 3 and 6 months (a HR of 1 versus chemotherapy for the first 3 or 6 months) followed by a constant HR of 0.56 (see Table 5.2.1-1). With 12 months minimum follow-up it is expected that the number of events will range between 497 and 506 respectively and the power will range between approximately 99% and 60% with a Type I error of 2% (two-sided) (see Table 5.2.1-2).

The primary PFS analysis will be based on all the events observed at time of database lock.

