8.1.4 Sample Size: Nivolumab plus Chemotherapy vs Chemotherapy

Progression Free Survival

All concurrently randomized subjects to N+CT and CT arms with PD-L1 CPS \geq 5 will be used for the PFS analysis. Given the delayed separation in the PFS distributions between pembrolizumab + chemotherapy and chemotherapy, ⁷⁶ the PFS analysis will be conducted after a minimum of 12 months follow-up after the last patient is randomized.

As such, the PFS analysis will be conducted after the following criteria are all met:

- CPS scoring by central laboratories is complete
- a minimum follow-up of 12 months

Based on the observed delay in the PFS KM curved of Pem+CT vs. CT, the HR is modelled as a 2-piece hazard ratio with a delayed effect between 3 and 6 months (a HR of 1 versus chemotherapy for the first 3 or 6 months) followed by a constant HR of 0.56 (see Table 8.1.4-1). With 12 months

minimum follow-up it is expected that the number of events will range between 497 and 506 respectively and the power will range approximately between 99% and 60% with a Type I error of 2% (two-sided) (See Table 8.1.4-2).

The primary PFS analysis will be based on all the events observed at time of database lock.

Table 8.1.4-1: Assumed PFS Hazard Rates and Hazard Ratios (Nivolumab plus Chemotherapy vs Chemotherapy)

Periods	Hazard Rates for Chemotherapy	Hazard Ratios (3 months delay)	Hazard Ratios (6 months delay)s
0-3 months	0.09	1	1
3-6 months	0.17	0.56	1
6-10 months	0.2	0.56	0.56
> 10 months	0.13	0.56	0.56

Table 8.1.4-2: Summary of Sample Size Parameters and Schedule of Analyses for PFS (Nivolumab plus Chemotherapy vs Chemotherapy)

	3 months Delay	6 months Delay
# subjects with PD-L1 CPS ≥5 ^a	554	554
Hypothesized delayed period	3	6
Hypothesized HR after delayed period	0.56	0.56
Hypothesized median in control arm	5.5 months	5.5 months
Significance level (2-sided)	0.02	0.02
Enrollment Period (from start of 1:1:1)	25.4 months	25.4 months
Minimum follow-up / Expected number of events ^{a,b,c}	12 months / 497	12 months / 506
Time of Analysis	37.4 months	37.4 months
Power ^b	99%	60%
Average HR ^b	0.66	0.8

a Based on 35% prevalence of PD-L1 CPS≥5

b Results based on simulations.

^c Number of events for the nivolumab plus chemotherapy vs. chemotherapy comparison in total.

Overall Survival

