**Table 5.2.1-1: PFS Hazard Rates and Hazard Ratios (Nivolumab plus Chemotherapy vs. Chemotherapy)**

Periods	Hazard Rates for Chemotherapy	Hazard Ratios (3 months delay)	Hazard Ratios (6 months delay)
0-3 months	0.09	1	1
3-6 months	0.17	0.56	1
6-10 months	0.2	0.56	0.56
> 10 months	0.13	0.56	0.56

**Table 5.2.1-2: Summary of Sample Size Parameters and Schedule of Analyses for PFS (Nivolumab plus Chemotherapy vs. Chemotherapy)**

	3 months Delay	6 months Delay
# subjects with PD-L1 CPS $\geq 5^a$	554	554
Hypothesized delayed period	3	6
Hypothesized HR after delayed period	0.56	0.56
Hypothesized median in control arm	5.5 months	5.5 months
Significance level (2-sided)	0.02	0.02
Enrollment Period (from start of 1:1:1)	25.4 months	25.4 months
Minimum follow-up / Expected number of events a,b,c	12 months / 497	12 months / 506
Time of Analysis	37.4 months	37.4 months
power b	99%	66%
average HR b	0.66	0.80

a Based on 35% prevalence of PD-L1 CPS  $\geq 5$

b Results based on simulations.

c Number of events for the nivolumab plus chemotherapy vs. chemotherapy comparison in total.

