**Figure 7.5.1-1: Graphical Approach for Primary and Secondary Endpoints**

In the graph, each vertex corresponds to a hypothesis to be tested. The square represent the hypotheses for the primary endpoints and the circles for secondary endpoints, light blue color represent comparison for nivo+ipi vs. chemo and dark blue represent comparison of nivo+chemo vs. chemo. The numbers next to the vertices are the initially allocated (endpoint-specific) significance levels. It is 0 for all secondary endpoints meaning that they cannot be tested until alpha is passed to them from the primary endpoints. The weight (in rectangular frame) associated with a directed edge (line) between any two vertices indicates the fraction of the (local)

significance level at the initial vertex that is added to the significance level at the terminal vertex, if the hypothesis at the tail is rejected.

Table 7.5.1-1 shows the significance levels for the primary and key secondary endpoints. For endpoints which have an interim analysis, the significance level will be distributed using the Lan-DeMets alpha spending function with O'Brien-Fleming boundaries. The nominal significance levels for OS in randomized PD-L1 CPS  $\geq 5$  subjects in Table 7.5.1-1 are those obtained with the number of events exactly as in the table and assuming a prevalence rate of 35% for PD-L1 CPS  $\geq 5$ . At time of analysis, the significance levels will be adjusted according to actual number of events and using the estimated final number of events. For interim analyses of OS in randomized PD-L1 CPS  $\geq 1$  subjects and all randomized subjects, the nominal significance levels will be obtained using the same information fraction as for randomized PD-L1 CPS  $\geq 5$  subjects. At the final analysis the significance level will be calculated using the number of events in the database at time of database lock and considering the  $\alpha$ -level already spent at interim analysis as well as the actual correlation among the test statistics.

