### **7.5.2.9 Secondary Efficacy Endpoints**

#### **Overall Survival in CPS $\geq 1$ subjects and All Randomized Subjects**

If the OS primary endpoint in randomized CPS  $\geq 5$  subjects is significantly superior then OS in randomized CPS  $\geq 1$  subjects will be compared using a two-sided log rank test and a significance level of 1.5%, stratified by the stratification factors as specified in [Table 7.5-1](#). Similarly if OS testing in randomized CPS  $\geq 1$  subjects is significantly superior then OS in all randomized subjects (all comers) will be compared using a two-sided log rank test and a significance level of 1.5%, stratified by the stratification factors as specified in [Table 7.5-1](#).

The stratified hazard ratio between the treatment groups will be presented along with 100\* (1 -  $\alpha$ )% CI (adjusted for interim). In addition, two-sided p-value will also be reported for the analysis of OS.

OS will be estimated using the KM techniques. A two-sided 95% CI for median OS in each treatment group will be computed via the log-log transformation method. OS rates at fixed time points (eg, 6, 12, 18, 24 months, depending on the minimum follow-up) will be presented along with their associated 95% CIs. These estimates will be derived from the Kaplan Meier estimate and corresponding CIs will be derived based on Greenwood formula for variance derivation and on log-log transformation applied on the survivor function.

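### SAP Table 5.2.1-2 prints 66% PFS power under the 6-month delay; the SAP text, the protocol and the stated hazards all give 60%

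*SAP*

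**What the plan says.** **PFS power.** SAP Section 5.2.1 states that "the power will range between approximately 99% and 60% with a Type I error of 2% (two-sided"), for delays of 3 and 6 months respectively, and points to Table 5.2.1-2. Both columns of that table have 554 subjects ("Based on 35% prevalence of PD-L1 CPS" ≥ 5), a hazard ratio of 0.56 after the delay, a control median of 5.5 months, 25.4 months of enrolment, 12 months of minimum follow-up and two-sided alpha 0.02. The expected events are 497 and 506. The power row reads 99% and 66%.

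Protocol Section 8.1.4 says "the power will range approximately between 99% and 60% with a Type I error of" 2%. Protocol Table 8.1.4-2 and Table 1 of the synopsis both print 99% and 60% for the same inputs. SAP Section 5.2 adds, under the software heading: "Sections 5.2.1 and 5.2.2 describe the sample size and power as stated in protocol".

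**Secondary OS level.** SAP Section 7.5.2.9 says that nivo+chemo OS in CPS ≥ 1 subjects "will be compared using a two-sided log rank test and a significance level of 1.5%, stratified by the stratification factors", and uses the same 1.5% for all randomized subjects. Section 7.5.1 says that for endpoints with an interim analysis "the significance level will be distributed using the Lan-DeMets alpha spending function". It names these two OS tests and gives them the CPS ≥ 5 information fraction.

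**The concern.** The text and the table of one SAP section give two power figures for one scenario, and the text cites the table as its source. The section claims to carry over the protocol's figures, so 66% cannot be read as a deliberate update. The 6-month delay is the less favourable PFS scenario, and delayed separation of the curves was a stated reason for Amendment 29's change of timing. A reader who takes the table at face value credits the 35%-prevalence design with more power than the protocol claimed for it.

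The secondary OS wording raises a lesser question. Section 7.5.2.9 gives 1.5% without saying whether it is the total for the test or the threshold at each look, and Table 7.5.1-1 has no column for these two endpoints.

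**Working it through.** **Inputs**
- Control PFS hazards per month (SAP Table 5.2.1-1, Protocol Table 8.1.4-1): 0.09 (months 0–3), 0.17 (3–6), 0.20 (6–10), 0.13 (after 10).
- Effect, 6-month delay: hazard ratio 1 to month 6, then 0.56.
- Subjects: 0.35 × 1582 = 553.7, so 554, randomized 1:1.
- Alpha 0.02 two-sided ("Significance level (2-sided) 0.02 0.02"); critical value 2.326.
- Timing: 25.4 months of accrual plus 12 months of follow-up, analysis at 37.4 months.
- Accrual (SAP Section 2.1): 1098 subjects at 1:1:1 from 27-Mar-2017 to 05-Jun-2018 (about 14.3 months), of whom 1098 × 2/3 = 732 fall in the two arms, then 850 at 1:1; 732 + 850 = 1582.
- Dropout: none stated, so zero assumed, with a range below.

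**Step 1. Control median.** Cumulative hazard at month 3 is 3 × 0.09 = 0.27. The median is 3 + (0.693 − 0.27)/0.17 = 5.49 months, matching the stated 5.5.

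**Step 2. The undisputed scenario (3-month delay).** Log-rank simulation with the documented accrual gives 496 events and 99.1% power. The plan states 497 and 99%, so the model matches the sponsor's.

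**Step 3. The disputed scenario (6-month delay).**

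| Run, alpha 0.02 unless noted | Events | Average HR | Power |
|---|---|---|---|
| SAP and protocol text, protocol tables | 506 | 0.80 | 60% |
| SAP Table 5.2.1-2 | 506 | 0.80 | 66% |
| Simulation, documented accrual (20,000 trials) | 504 | 0.79 | 59.9% |
| Simulation, uniform accrual (10,000 trials) | 509 | 0.79 | 61.5% |
| Documented accrual, alpha 0.03 | 504 | 0.79 | 65.9% |

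The Monte Carlo standard error of the 59.9% is √(0.6 × 0.4/20,000) = 0.35 points, so 66% lies far outside simulation noise. Other zero-dropout runs at alpha 0.02 with these two accrual patterns gave 58.7% to 63.0%; none reached 66%. Under uniform accrual, dropout of 0.003, 0.005 and 0.01 per month lowers power to 59.4%, 57.6% and 53.2%. Allowing for dropout therefore moves the figure away from 66%.

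**Step 4. Closed-form check.** Schoenfeld: power = Φ(|ln HR| × √events / 2 − 2.326). With HR 0.80 and 506 events: 0.2231 × 22.49 / 2 = 2.510, and Φ(2.510 − 2.326) = 57.3%. An average HR of 0.795, which also rounds to 0.80, gives 60.0%. For 66% the average HR would have to be exp(−2 × (2.326 + 0.412)/22.49) = 0.784, which does not round to the 0.80 in the table. The formula assumes proportional hazards, so the simulation carries the weight.

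**Step 5. Levels behind the optional clarification.** The 1.5% is 0.03/2, the share passed on when CPS ≥ 5 OS is significant. O'Brien-Fleming-type spending, with a = alpha/2 per side, spends 2[1 − Φ(z(1 − a/2)/√t)] per side by fraction t. As a check on the plan's own figures, alpha 0.03 at t = 395/466 = 0.848 gives 0.0165 and 0.0252, against 0.0164 and 0.0252 stated. For alpha 0.015 at t = 680/800 = 0.85, the interim level is 2 × 2[1 − Φ(2.674/0.922)] = 0.0075. The final level, from the bivariate normal with correlation √t, is 0.0128. A literal 1.5% at both looks would spend 2.13%.

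**The case against.** The strongest reply is that the cell no longer matters. Appendix 5 states that Table 5.2.1-2 is updated by its own Table 1, based on the observed 60% prevalence: 949 subjects, 857 events and 84.0% power for the 6-month delay. Enrolment was complete and the analyses were time-driven, so nothing was sized or timed on 66%. The PFS analysis had also been carried out before this SAP version was issued. All of this stands. It limits the consequence but does not make the cell right: Section 5.2.1 remains in the current SAP as the record of the protocol design, and there it contradicts itself.

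On the secondary OS tests, a reader might infer that the SAP applies a flat 1.5% at both looks and so spends 2.13%. The documents do not support that. Section 7.5.1 applies the spending function to endpoints with an interim and names exactly these two tests. The 1.5% is half of the 0.03 passed on, hence the total for that branch. Section 7.5.2.9 itself calls the confidence interval adjusted for the interim. Nivo+ipi OS is tested once, so the question does not arise there.

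A reader might also object that Appendix 5 Table 2 keeps 0.0164 and 0.0252 while the events move to 680/800. The fraction changes only from 0.848 to 0.850. The final level is unchanged and the interim would be 0.0167, and Appendix 5 and the table's footnote say levels are recalculated from actual deaths. That is not a fault to pursue.

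**Conclusion.** The 6-month-delay power in SAP Table 5.2.1-2 is wrong as printed and should be 60%. It overstates the protocol's figure by 6 percentage points at 554 subjects and two-sided alpha 0.02. The conclusion rests on the SAP's own text, the protocol's text and tables, the SAP's statement that the section restates the protocol, and simulation from the stated hazards with zero dropout assumed. The same simulation gives 65.9% at alpha 0.03, the OS allocation, so a run at the wrong alpha is one possible origin; the documents do not say.

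This is a minor correction. A reader might infer that the operative power of the PFS analysis was overstated. That does not follow: the operative figure is the 84.0% in Appendix 5, and simulation at 949 subjects gives about 86%. The wording in Section 7.5.2.9 is a missing cross-reference; it is not evidence of an inflated error rate.

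**What to change.** In SAP Table 5.2.1-2, change the 6-month-delay power from 66% to 60%. The text of Section 5.2.1 and the protocol need no change. The cost is one table cell; no analysis, threshold or sample size is affected.

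Optionally, in SAP Section 7.5.2.9, describe 1.5% as the overall two-sided alpha for nivo+chemo OS in CPS ≥ 1 subjects and in all randomized subjects, divided between interim and final by the rule in Section 7.5.1. If levels are shown, about 0.0075 and 0.0128 at an information fraction of 0.85 would serve, labelled as illustrative because the levels actually used depend on observed events. This is one sentence and leaves the testing rule unchanged.
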